9.8. FOLLOW UP OF SERIOUS ADVERSE EVENTS

[figure not shown]
Centres should continue to follow up SAEs until clinical recovery is complete and laboratory results have returned to normal, or until disease has stabilised. SAE outcomes should be reported to ICR-CTSU using the relevant section of the SAE form as soon as the Principal Investigator becomes aware of the outcome.

NB. Any female patient who becomes pregnant or the partner of any male patient who fathers a child whilst on study medication, must be followed up and the outcome reported to ICR-CTSU who will then forward the details to Pfizer.

9.9. ANNUAL REPORTING OF SERIOUS ADVERSE REACTIONS

An annual report will be provided to the MHRA and the Main REC by ICR-CTSU and copied to the sponsors at the end of the reporting year. This will be defined as the anniversary of the date when the Clinical Trials Authorisation (CTA) was obtained. This will include all related events reported on SAE forms, and a report from the Independent Data Monitoring and Steering Committee (IDMSC).

9.9.1. FIGURE 3 - FLOW DIAGRAM FOR SAE REPORTING, AND ACTION FOLLOWING REPORT

NB. All SAEs should continue to be followed up as specified in the protocol.

10. STATISTICAL CONSIDERATIONS

10.1. STATISTICAL DESIGN AND SAMPLE SIZE JUSTIFICATION

This study is designed to assess the efficacy of axitinib in patients with mRCC not immediately clinically indicated for nephrectomy, a very poor risk group of patients. The median progression free survival for poor risk patients with mRCC treated with temsirolimus, the standard of care in this setting, is approximately 5.5 months[17]. Some benefit is expected for patients treated with axitinib, but the

expected degree of benefit is not known, nor is it known whether there will be a benefit via an increased response rate, or a prolongation of response, or both, detectable in PFS at 6 months.

Using a Simon Optimal Two-Stage design this study has 90% power at a one-sided significance level of 0.05 to discount an 'ineffective' rate of freedom from progression at 6 months (PFS6) of 25% (p_0) in favour of a PFS6 of at least 40% (p_1). This point estimate (40%) is lower than perhaps expected for temsirolimus (ignoring the inevitable variability around these estimates). However, a slightly lower threshold for axitinib may be acceptable given it is well tolerated and an oral compound, thus requiring fewer visits to hospital than for an IV drug such as temsirolimus.

37 patients will be treated in stage one and, if successful, a further 62 patients in stage two bringing the total number of patients required to 99. There will be no planned stopping in recruitment between stages 1 and 2; patients will be entered into stage 2 whilst stage 1 patients are progressing through the trial, their data being analysed and reviewed by the Independent Data Monitoring and Steering Committee (IDMSC).

The trial will stop and the treatment will be rejected if there are fewer than 11 patients alive and progression free at 6 months when the first 37 patients have been on trial for 6 months. If 11 or more of the first 37 patients are alive and progression free at 6 months a further 62 patients will be recruited into the second stage. If there are 32 or more patients of the overall 99 entered alive and progression free at 6 months axitinib will be considered to have shown worthwhile efficacy, but not if there are 31 or less. Planning for a phase III trial can commence at any stage if 32 patients have been observed to be alive and progression free at 6 months. No data will be released from stage 1 whilst recruitment to stage 2 is ongoing unless advised to do so by the IDMSC.

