10.3. INTERIM ANALYSIS AND DATA MONITORING

An Independent Data Monitoring Committee will meet approximately every 6 months to review accrual, safety and efficacy data. The subsequent replacement of patients who withdraw from treatment or who are unevaluable for reasons deemed not to be treatment related will be based on the advice of this committee. For completeness a sensitivity analysis of the progression free rate calculated by the Kaplan Meier product limit method will also be presented in which withdrawals are censored.

A formal interim analysis will be conducted once the first 37 patients have at least 6 months follow up data available. The principal analysis for publication will occur on the recommendation of the IDMSC and is expected once 99 patients have at least 6 months follow up data available (or have died).

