11.2. INDEPENDENT DATA MONITORING AND STEERING COMMITTEE (IDMSC)

The roles of the IDMC and TSC will be combined, i.e. the committee will both monitor the data produced by the trial, put these data into overall context and supervise the progress of the trial towards its interim and overall objectives. This committee will be constituted according to MRC Good Clinical Practice (MRC GCP) and will oversee the safety of the trial.

The IDMSc will meet in confidence at regular intervals, and at least annually. A report of the findings and recommendations will be produced following each meeting. This report will be submitted to the TMG and if required, the main REC and the MHRA.

The IDMSc reserve the right to release any data on outcome or side-effects to the TMG (and if appropriate to participants) if it determines at any stage that the combined evidence from this and other studies justifies it.

The Committee's terms of reference, roles and responsibilities will be defined in a charter issued by ICR-CTSU.

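### The stage-1 futility rule is read only when all 37 patients reach 6 months, with recruitment open and no trigger for the earlier moment when 27 week-25 failures have already fixed the outcome

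*Combined protocol and SAP*

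**What the plan says.** Section 10.1 specifies a Simon optimal two-stage design with "90% power at a one-sided significance level of 0.05", for a 6-month progression-free rate of 25% against 40%. "37 patients will be treated in stage one and, if successful, a further 62 patients in stage two". Success needs 32 or more of 99.

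The stage-1 rule rejects the treatment on this result: "fewer than 11 patients alive and progression free at 6 months when the first 37 patients have been on trial for 6 months". On accrual, the section says: "There will be no planned stopping in recruitment between stages 1 and 2". Section 10.3 places the look at the same point: "A formal interim analysis will be conducted once the first 37 patients have at least 6 months follow up data available".

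Section 10.3 also has the independent committee review accrual, safety and efficacy about every 6 months, and 11.2 sets a minimum meeting frequency: "The IDMSc will meet in confidence at regular intervals, and at least annually". Neither section states a result that would trigger an earlier stop. Section 10.2.1 defines the endpoint as status at the day 1 week 25 visit and requires confirmed progression.

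**The concern.** The rule waits for the 37th patient's 6-month status, but the answer is often known before then. Once 27 of the first 37 have failed by week 25, at most 37 − 27 = 10 can succeed and the boundary of 11 is out of reach. Patients entered after that moment join a trial whose own rule has already been decided. Section 10.1 calls this a very poor risk group, and entry carries a mandatory biopsy of the primary tumour (7.1.1), with another scheduled at week 9 (7.6).

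The optimal version of Simon's design minimises expected sample size under the null. Continuous recruitment gives up part of that saving. Acting when the result is certain recovers some of it without a pause.

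**Working it through.** **Inputs from the protocol.** First stage 37, total 99; stop at 10 or fewer successes, succeed at 32 or more (10.1). Rates 25% and 40% (10.1). Scans on day 1 of weeks 9, 17 and 25, then every 12 weeks (7.6, 7.7). Endpoint at week 25, which is 24 weeks or 24/4.345 = 5.52 months (10.2.1).

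**Assumptions.** Accrual of 1 to 8 patients a month (none is given), random entry, exponential progression-free survival scaled to the stated 24-week rate, failures found at scheduled scans, and no committee delay.

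**Step 1: reproduce the design (exact binomial).**
- Probability of stopping at stage 1 = P(X ≤ 10), X ~ Bin(37, p): 0.691 at 25%, 0.072 at 40%.
- P(success) = Σ over x = 11 to 37 of P(X = x) × P(Y ≥ 32 − x), Y ~ Bin(62, p): 0.0493 at 25%, 0.9002 at 40%.
- Expected N at 25% with a pause = 37 + 62 × (1 − 0.691) = 56.2.

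The stated design is confirmed.

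**Step 2: curtailment leaves the error rates alone.** P(10 or fewer successes of 37 at 25%) = P(27 or more failures of 37 at 75%) = 0.691. The two events are identical, so acting on the 27th week-25 failure changes no decision.

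**Step 3: lead time and entries spared.** These are simulated at a true rate of 25%, among trials that fail stage 1. The comparison is the 27th detected failure against the 37th patient's week 25.

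| Accrual per month | Mean lead (months) | Mean entries spared | 10th to 90th percentile |
|---|---|---|---|
| 1 | 5.1 | 5.1 | 1 to 10 |
| 2 | 3.5 | 6.9 | 1 to 13 |
| 4 | 2.5 | 9.9 | 2 to 18 |
| 6 | 2.0 | 12.1 | 2 to 22 |
| 8 | 1.7 | 13.5 | 2 to 25 |

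Failure is certain before the planned look in about 97% of these trials. Averaged over all trials at 25%, the saving is 0.691 × 6.9 = 4.8 at 2 a month and 0.691 × 12.1 = 8.4 at 6 a month.

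**Step 4: expected N at 25%.** Without a pause it is 0.691 × (37 + 5.52 × rate) + 0.309 × 99, which gives 63.8, 71.4 and 79.0 at 2, 4 and 6 a month. Curtailment takes off 0.691 × (6.9, 9.9, 12.1) = 4.8, 6.8 and 8.4, leaving about 59, 65 and 71.

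**Step 5: sensitivity (2 to 6 a month).**
- A one-month reporting lag on the early trigger only: about 5 to 7 spared.
- Weibull shape 0.8: 7.5 to 13.5. Shape 1.3: 6.2 to 10.1.
- Endpoint at 6.0 months: 7.2 to 12.2.
- True rate 40%: about 5 to 7, but stage 1 then fails in only 7% of trials.

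**Step 6: why the trigger needs a week-25 limit.** When the 37th patient reaches week 25, early entrants have been followed well beyond it. A patient who is progression free at week 25 and progresses at the next scan is a success under 10.2.1. If any progression known by the time of the look is counted (even entry), the chance of a stage-1 stop at a true rate of 40% rises from 7% to about 98%, 64% and 35% at 2, 4 and 6 a month. Power cannot exceed one minus these figures: about 2%, 36% and 65%.

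**The case against.** The strongest reply is that continuous recruitment is a disclosed choice, the Simon design is correctly specified, and the committee already sees efficacy data. Section 10.1 has it reviewing stage-1 data while stage 2 fills, 10.3 provides a review about every 6 months, and 11.2 asks it to supervise progress towards interim objectives. This stands in part: the committee could recommend an earlier stop. But it has no written criterion. Even if every 6-monthly look acted on certainty, those looks would save only about 2.5 entries, leaving roughly 4 to 10 of the 7 to 12.

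A second objection also stands. Certainty is conditional. Progression must be confirmed, equivocal findings wait for the next scan (Appendix A, 18.7), scans are centrally verified (10.2.1), and withdrawn or unevaluable patients may be replaced (10.3). A raw count of 27 could later fall, so the trigger must count confirmed failures after any replacement.

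Three stronger readings are tempting, and the documents do not support them.
- A reader might infer that the plan allows early action for success but not for failure, because "Planning for a phase III trial can commence at any stage if 32 patients have been observed". That sentence permits planning of another trial. It neither stops recruitment nor ends this one.
- A reader might see a conflict between reviews about every 6 months (10.3) and meetings at least annually (11.2). The first satisfies the second, and the formal interim is triggered by follow-up, not by the meeting calendar.
- A reader might take 7 to 12 patients as a property of the plan. It depends on an accrual rate that the documents do not give.

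**Conclusion.** The point holds as a cheap improvement, not as an error in the design. The rule as written waits for all 37 patients, recruitment stays open, and nothing says to act once 27 week-25 failures make 11 successes impossible.

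The saving averages about 7 to 12 entries and 3.5 to 2.0 months, given a true rate of 25%, a failed stage 1 and 2 to 6 patients a month. The mean is 5 to 13.5 over 1 to 8 a month. Individual trials vary widely, and reporting lag reduces the gain. The accrual range is the main unknown. The exact results (0.0493, 0.9002, 0.691) need no such assumption.

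The protocol is Version 9, dated 2020, and does not say whether accrual is closed. If it is, the change can no longer spare anyone in this trial.

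**What to change.** Add to 10.1:

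> The stage-1 futility rule is met, and recruitment stops, as soon as 27 of the first 37 patients (after any replacement advised by the IDMSC) have died or had confirmed RECIST 1.1 progression on or before their own day 1 week 25 assessment. Progression after a progression-free week-25 assessment does not count. ICR-CTSU keeps a running count and convenes the IDMSC promptly when the 27th such failure is recorded, or when the 37th patient reaches week 25 if that is earlier.

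State also that all entered patients continue to be followed, so that the 6-month rate is still estimated. The text governs recruitment and leaves the treatment of patients already entered to the existing sections. Sections 10.3 and 11.2 need no alignment.

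The cost is a few sentences, a running count of events already collected in the eCRF, and possibly one ad hoc committee meeting. Type I error, power and the probability of early stopping are unchanged.

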1.3. PATIENTS PRESENTING WITH METASTATIC DISEASE NOT CLINICALLY INDICATED FOR NEPHRECTOMY

A significant number of patients presenting with metastatic disease are not treated with palliative nephrectomy. There are a number of reasons for this including comorbidity, technically inoperable disease, the presence of a significant volume of metastatic disease, the presence of metastatic disease in multiple or particular sites (e.g. liver) and the presence of other poor risk factors e.g. serum LDH>ULN, hypercalcaemia, anaemia and poor performance status (PS). Outcomes are generally extremely poor in this group. The strongest evidence base for systemic treatment in this group is for the mTOR inhibitor temsirolimus, a drug not approved by the National Institute for Health and Clinical Excellence (NICE) for use in the UK. In a phase III study [17] patients with at least 3 of 6 poor risk factors (time from diagnosis of metastatic disease to

therapy <12 months, 2 or more organ sites of metastatic disease, poor PS, raised LDH, hypercalcaemia or anaemia) were randomized to interferon, temsirolimus or the combination of the drugs. Approximately a third of patients had not undergone prior nephrectomy. Outcomes were best in the temsirolimus only group, compared to the interferon and combination groups, with a median progression-free survival (PFS) of 5.5 months and median overall survival (OS) of 10.9 months; as a consequence, temsirolimus is the preferred treatment choice in this group. Patients in this group in the UK may be offered either sunitinib (despite the fact that the evidence base for its use in this group is limited) or best supportive care alone. There is a clear need for improved outcomes in this group of patients and to identify mechanisms of sensitivity and resistance to VEGF-targeted therapy.

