10.2. ENDPOINT DEFINITIONS

10.2.1. PRIMARY ENDPOINT

The proportion of study participants alive and progression free at 6 months (day 1 week 25 visit). Progression will be measured from the date of study entry (registration date) until the first date of either death or confirmed progressive disease according to RECIST. Patients alive and free from progression will be censored at the date of last follow-up. The proportion of patients progression free at 6 months will be reported with 95% confidence interval. In addition, progression free survival will be presented using the Kaplan Meier product limit method with median progression free survival reported.

A blinded central review of CT scans will be conducted for verification purposes.

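### Does the unspecified 95% interval contradict the 32-of-99 success rule, and does that pass mark undercut the 'slightly lower threshold' argument?

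*Combined protocol and SAP*

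**What the plan says.** Section 10.1 describes a Simon optimal two-stage design with one-sided significance level 0.05 and 90% power. It tests an ineffective six-month rate of 25% (p0) against 40% (p1). The trial continues if at least 11 of the first 37 patients succeed. With 32 or more successes among 99, "axitinib will be considered to have shown worthwhile efficacy, but not if there are 31 or less". The same count has a practical use: "Planning for a phase III trial can commence at any stage if 32 patients have been observed to be alive" and free of progression at that time.

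Section 10.2.1 gives the reporting: "The proportion of patients progression free at 6 months will be reported with 95% confidence interval". It names no method, and it does not say how the interval relates to the rule in 10.1. Sections 10.2.2 and 10.3 do not add this.

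On the choice of 40%, section 10.1 cites a median progression-free survival of about 5.5 months on temsirolimus. It then says: "This point estimate (40%) is lower than perhaps expected for temsirolimus (ignoring the inevitable variability around these estimates"). It goes on: "a slightly lower threshold for axitinib may be acceptable given it is well tolerated and an oral compound".

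**The concern.** There are two grounds for suspicion.

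First, a trial with 32 or 33 successes would be declared to show worthwhile efficacy, and phase III planning could begin. Its published 95% interval would still contain the rate that the plan itself calls ineffective. Because no method is named, it also seems that agreement between interval and verdict could be settled after the data are seen.

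Second, the argument for a slightly lower threshold is made at 40%, while success is triggered at 32/99 = 32.3%. A median of 5.5 months suggests something near 47% to 50% progression-free at six months. On that reading the operative bar would be 15 to 18 points below temsirolimus, which is hardly slight, and a reader could overrate a borderline success.

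**Working it through.** **Inputs.** From 10.1: p0 = 0.25, p1 = 0.40, one-sided 0.05, power 90%, continue at 11 or more of 37, succeed at 32 or more of 99, temsirolimus median 5.5 months. From 10.2.1: a 95% interval, with the assessment at day 1 of week 25, which is 24 × 7 = 168 days, or 5.52 months.

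**1. The design.** The probability of success at true rate p is

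W(p) = Σ (x = 11 to 37) Bin(x; 37, p) × P[Bin(62, p) ≥ 32 − x].

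This gives W(0.25) = 0.0493 and W(0.40) = 0.9002. The chance of stopping at stage 1 when p = 0.25 is 0.691. A search for the smallest expected sample size under p0 returns the same design (10/37, 31/99). The stated figures hold.

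**2. Lower limits near the boundary.** The two-stage exact limit is the p at which the two-stage tail probability equals 0.025 (95% interval) or 0.05 (90% interval).

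| Count of 99 | Ordinary exact 95% | Wilson 95% | Wald 95% | Two-stage exact 95% | Two-stage exact 90% | Two-stage one-sided p against 25% |
|---|---|---|---|---|---|---|
| 31 | 0.2236 | 0.2302 | 0.2218 | 0.2288 | 0.2422 | 0.0710 |
| 32 | 0.2327 | 0.2392 | 0.2311 | 0.2368 | 0.2503 | 0.0493 |
| 33 | 0.2418 | 0.2482 | 0.2405 | 0.2450 | 0.2586 | 0.0327 |
| 34 | 0.2509 | 0.2573 | 0.2499 | 0.2534 | 0.2670 | 0.0207 |

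The last column explains the pattern. A two-sided 95% lower limit corresponds to a one-sided 2.5% test, and the rule is a one-sided 5% test. The counts with p between 0.025 and 0.05 are exactly 32 and 33. Once level and stage structure both match the rule (two-stage exact, 90%), interval and rule agree: 25% is inside at 31 and outside at 32.

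**3. How far the method matters.** The ordinary exact, Wilson and two-stage exact 95% intervals all change sides at 34. Two other choices shift this by one count. Wald at 34 gives 0.3434 − 1.96 × √(0.3434 × 0.6566 / 99) = 0.2499, just including 25%. A log-scale interval at 33 gives exp[ln(0.3333) − 1.96 × √(0.6667 / 33)] = 0.252, just excluding it. The 95% level is fixed in 10.2.1, so a later move to 90% is not open.

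**4. How often it arises.** Probability of passing with exactly 32 or 33:

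| True rate | P(32 or 33, stage 1 passed) | P(success) | Share of successes |
|---|---|---|---|
| 25% | 0.0286 | 0.0493 | 58% |
| 30% | 0.1076 | 0.2870 | 37% |
| 35% | 0.1170 | 0.6621 | 18% |
| 40% | 0.0444 | 0.9002 | 5% |

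The maximum over all true rates is about 13%.

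**5. Is the ordinary interval misleading under two stages?** Coverage of the ordinary exact 95% interval, with the stage 1 stop included, is about 94% or above for true rates from 15% to 60%.

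**6. The temsirolimus comparison.** The documents give only a median, so a six-month rate needs an assumption about shape.
- Exponential, week-25 visit: 0.5^(5.52/5.5) = 0.499.
- Exponential, six calendar months: 0.5^(6/5.5) = 0.469.
- Weibull with shape 2, six calendar months: 0.5^((6/5.5)²) = 0.438.

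Against this range of 44% to 50%, the 40% target is about 4 to 10 points lower. The 32.3% figure is an observed proportion, not a true rate that the trial is built to accept: W(0.323) = 0.46, against W(0.40) = 0.90. A drug whose true rate equals the pass mark fails more often than it passes.

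**The case for a change.** The best case for a change is that the narrow band matters most for a weak drug. If the true rate is 25%, 58% of the false successes land on 32 or 33, and at 30% it is 37% of successes. These are the results for which a reader most needs interval and verdict to agree, and 32 is also the count that opens phase III planning. One sentence naming a two-stage exact method, plus a 90% interval, would bring them into line at no cost in patients or data. Section 10.1 also never sets 32.3% beside temsirolimus.

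Part of this stands. The method is not named, and a matched 90% two-stage interval would agree with the rule. But the false successes at 25% are already counted in the 4.9% error that the design accepts, and showing another interval removes none of them. In the borderline cases the wider 95% interval tells the reader that the evidence is thin, which is useful information. The second interval and a stage-adjusted estimate are reporting preferences, and the estimate has no single agreed convention: at 32/99 it is 32.8% if median-unbiased and 35.0% if minimum-variance unbiased.

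The temsirolimus part is weaker. The word threshold follows directly on the 40% figure and refers to it. The benchmark is inferred from a median, and its patients differ from this trial's in ways that could bias either way. They were "patients with at least 3 of 6 poor risk factors", yet "Approximately a third of patients had not undergone prior nephrectomy", so about two thirds had.

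**Conclusion.** No change follows. The sample size, error rates and cut-offs in 10.1 are right, and the count alone decides. Nothing in 10.2.1 gives the 95% interval a role in the decision, so its overlap with 25% at 32 and 33 is a difference of level and not a contradiction. A pass with one of these counts has a 4.4% chance at the design's target rate and at most about 13% at any rate. The unnamed method is a gap that an analyst would fill with a standard exact or Wilson interval. Either has its lower limit cross 25% at 34, and the exact one covers adequately under the two-stage design.

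The remark about a slightly lower threshold describes the 40% target. Section 10.1 discloses that this is below what temsirolimus might achieve and gives a reason. Whether 4 to 10 points is slight is a matter of wording, and the size rests on an assumed shape of the survival curve. A pass mark below the target rate is built into a design with 90% power. Rewording it would alter nothing the trial does or concludes.

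These figures assume that 37 and 99 patients are analysed, as 10.1 plans.
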